10.1 Ethical Standard

The investigator will ensure that this study is conducted in full conformity with Regulations for the Protection of Human Subjects of Research codified in 45 CFR Part 46, 21 CFR Part 50, 21 CFR Part 56, and/or the ICH E6.

10.2 Institutional Review Board

The protocol, informed consent form(s), recruitment materials, and all participant materials will be submitted to the IRB for review and approval. Approval of both the protocol and the consent form must be obtained before any participant is enrolled. Any amendment to the protocol will require review and approval by the IRB before the changes are implemented to the study. All changes to the consent form will be IRB approved; a determination will be made regarding whether previously consented participants need to be re-consented.

CONFIDENTIAL

This material is the property of the NYU School of Medicine and Langone Medical Center. Do not disclose or use except as authorized in writing by the study sponsor

10.3 Participant and Data Confidentiality

Information about study subjects will be kept confidential and managed according to the requirements of the Health Insurance Portability and Accountability Act of 1996 (HIPAA). Those regulations require a signed subject authorization informing the subject of the following:

- What protected health information (PHI) will be collected from subjects in this study
- Who will have access to that information and why
- Who will use or disclose that information
- The rights of a research subject to revoke their authorization for use of their PHI.

In the event that a subject revokes authorization to collect or use PHI, the investigator, by regulation, retains the ability to use all information collected prior to the revocation of subject authorization. For subjects that have revoked authorization to collect or use PHI, attempts should be made to obtain permission to collect at least vital status (i.e. that the subject is alive) at the end of their scheduled study period.

Participant confidentiality is strictly held in trust by the participating investigators, their staff, and the sponsor(s) and their agents. Therefore, the study protocol, documentation, data, and all other information generated will be held in strict confidence. No information concerning the study or the data will be released to any unauthorized third party without prior written approval of the sponsor.

The study monitor, other authorized representatives of the sponsor, representatives of the IRB or pharmaceutical company supplying study product may inspect all documents and records required to be maintained by the investigator, including but not limited to, medical records (office, clinic, or hospital) and pharmacy records for the participants in this study. The clinical study site will permit access to such records.

The study participant's contact information will be securely stored at each clinical site for internal use during the study. At the end of the study, all records will continue to be kept in a secure location for as long a period as dictated by local IRB and Institutional regulations.

Study participant research data, which is for purposes of statistical analysis and scientific reporting, will be transmitted to and stored at NYU Langone Medical Center. This will not include the participant's contact or identifying information. Rather, individual participants and their research data will be identified by a unique study identification number. The study data entry and study management systems used by clinical sites and by NYU Langone Medical Center research staff will be secured and password protected. At the end of the study, all study databases will be de-identified and archived at the NYU Langone Medical Center.

11 Data Handling and Record Keeping

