Endpoint	Primary Endpoint: Opioid utilization for the first 72 hours after surgery, including during surgery, calculated as morphine equivalent. Secondary Endpoints: Opioid consumption Post-operatively Patient reported VAS scores in PACU Length of stay in PACU Patient reported VAS scores on POD 1, POD 2, POD 3, POD 7 Reaction to IPACK block Incidence of postoperative complications
Study Duration	The study will continue until 50 subjects are enrolled per arm, to allow for potential dropout and increased power.
Participant Duration	Each participant will be enrolled on DOS and complete their final follow up on postoperative day seven.
Duration of IP administration	Once during surgery
Population	50 patients per study arm scheduled for ACLR with BPTB autograft
Study Sites	NYU Langone Orthopedic Hospital and NYU Ambulatory Surgery Center at 38 th street
Number of participants	100
Description of Study Agent/Procedure	Patients in both the study and control group will receive the standard of care adductor canal block composed of 15 mL of Bupivacaine (0.25%). Patients in the study group will receive the additional IPACK block performed using 20 mL of Bupivacaine (0.25%) injected into the interspace between the popliteal artery and capsule of the knee. Patients will be blinded to their group allocation.
Reference Therapy	Reference is isolated adductor canal block
Key Procedures	Adductor canal block 15 mL 0.25% Bupivacaine, IPACK block with 20 mL 0.25% bupivacaine

CONFIDENTIAL

This material is the property of the NYU School of Medicine and Langone Medical Center. Do not disclose or use except as authorized in writing by the study sponsor

Statistical Analysis	Continuous and categorical baseline characteristics will be compared using Hedges standardized difference. Normally distributed data will be compared using t tests while non-normally distributed continuous outcomes will be assessed using the Mann-Whitney U test.
----------------------	--

CONFIDENTIAL

This material is the property of the NYU School of Medicine and Langone Medical Center. Do not disclose or use except as authorized in writing by the study sponsor

1 Background and Specific Aims

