TREATMENT PHASE:

Patients in both the study and control group will receive the standard of care adductor canal block. This consists of 15mL of bupivacaine (0.25%) Injected under ultrasound guidance in the saphenous nerve via the adductor canal. Patients in the study group will receive the additional IPACK block performed using 20 mL of bupivacaine (0.25%) injected into the interspace between the popliteal artery and capsule of the knee.

[figure not shown]
POST-OPERATIVE PHASE:

After initial recruitment, subjects' pain will be assessed via visual analog scale (VAS) by nursing staff during the post-operative period as per standard of care in the post anesthesia care unit, and by the research staff prior to leaving the surgical center. The VAS pain scores are collected and documented in the patient's electronic medical record. Additionally, a standardized regimen of pain medication will be given to all subjects who are enrolled. The pain medications given to patients are standard of care medication 325-5 mg Percocet and vary based on pain level. This is determined by the clinical staff caring for each patient. While the patient is in the PACU prior to discharge, an authorized research member will visit the patient and obtain a pain score using the VAS and McGill Pain Scale. Data on PACU opioid use documented in the electronic medical record will be collected. On POD1, POD 2 and POD 3, a phone call or email survey will be sent to the patient to collect additional data on opioid use at home as well as a VAS score at 24, 48, and 72 hours after surgery.

CONFIDENTIAL

This material is the property of the NYU School of Medicine and Langone Medical Center. Do not disclose or use except as authorized in writing by the study sponsor

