4.2.3 Follow-Up Phone call/message (POD 1, POD 2 and POD 3)

Phone call to patient to collect additional data on opioid use following discharge, on POD 1, POD 2 and 3 after surgery

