4.2.5 Withdrawal/Early Termination Visit

Subjects may discontinue their participation in the study at any time. As there is only a single intervention, and the safety of this is not in question, further follow up will not be required if a subject decides to terminate their participation in the study.

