6.2 Analysis of Endpoints

Primary Endpoints:

1. Opioid utilization for the first 24 hours after surgery, including during surgery, calculated as oral morphine equivalent.

CONFIDENTIAL

This material is the property of the NYU School of Medicine and Langone Medical Center. Do not disclose or use except as authorized in writing by the study sponsor

Secondary Endpoints:

1. Patient reported VAS scores in PACU
2. Length of stay in PACU
3. Patient reported VAS scores on POD 1, POD 2, POD 3, POD7
4. Reaction to IPACK block
5. Mid-term functional outcomes will be assessed at 6 months: VAS, KOOS-PS, KUJALA, Tegner Activity Scale, strength, ROM.

Normally distributed data such as the primary outcome variable will be compared using the two-sample t-test. In the case that the data are not normally distributed, the Wilcoxon rank-sum test will be used instead. Categorical variable will be compared using the Chi-Squares unless other tests such as the Fisher's exact test are more appropriate.

All endpoints will be evaluated as fits the data set with graphical figures such as scatter plots, box-and-whisker plots, and frequency histograms to visualize the distribution of these outcomes and their relationships to covariates and treatment assignment. When appropriate descriptive graphical and tabular methods will also be estimated and presented in a graphical figure.

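### Section 4.2.5 ends follow-up at voluntary withdrawal without asking for the remaining POD 1–3 opioid reports, so an early leaver can drop out of the ITT primary analysis

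*Combined protocol and SAP*

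**What the plan says.** Two sections deal with subjects who leave by choice, and they cover different events.

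- **Ending participation (4.2.5).** The section says that "further follow up will not be required if a subject decides to terminate their participation in the study". Its reasons are that there is one intervention and that its safety is not in doubt.
- **Revoking authorization to use health information (10.3).** The investigator "retains the ability to use all information collected prior to the revocation of subject authorization". For new data, "attempts should be made to obtain permission to collect at least vital status (i.e. that the subject is alive".

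The primary endpoint is total opioid use, and it comes from two sources. Use in the PACU comes from the chart: "Data on PACU opioid use documented in the electronic medical record will be collected" (2.1). Use at home comes from the subject: "a phone call or email survey will be sent to the patient to collect additional data on opioid use at home" (2.1), and section 4.2.3 lists "Phone call to patient to collect additional data on opioid use following discharge, on POD 1, POD 2 and 3 after surgery".

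The window is stated in two ways. The Protocol Summary gives "Opioid utilization for the first 72 hours after surgery, including during surgery, calculated as morphine equivalent", and section 1.3 agrees on 72 hours. Section 6.2 gives "Opioid utilization for the first 24 hours after surgery, including during surgery, calculated as oral morphine equivalent", and sections 1.2 and 6.1 also use 24 hours.

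Section 6.1 makes the primary analysis intention-to-treat, and section 3.6 promises the same for subjects lost to follow-up. Section 6.1 then removes any patient whose primary outcome cannot be established with reasonable certainty.

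**The concern.** The reasons given in 4.2.5 concern treatment and safety. They do not address measurement of the outcome. The block is over before most of the opioid use that the trial is designed to compare has occurred, so having no treatment left to give is no reason to stop asking about opioid use.

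An intention-to-treat comparison needs outcomes from people who leave. This plan has no step that asks for them, and it has a rule that removes patients whose outcome is missing. If subjects leave because pain control is poor, or because it is so good that the calls seem pointless, those removed differ from those kept. If that differs between arms, the estimated effect of the IPACK block is biased. Section 6 describes no imputation or sensitivity analysis that would show how far the result depends on those removed.

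**Working it through.** **Step 1. Which withdrawals lose primary data.** Assume discharge before 24 hours (the Background describes an ambulatory setting), and assume that each report covers use up to its own time point (2.1 ties the contacts to 24, 48 and 72 hours).

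| Subject ends participation | 24-hour endpoint | 72-hour endpoint |
|---|---|---|
| After discharge, before the POD 1 report | incomplete | incomplete |
| After the POD 1 report, before the POD 3 report | complete | incomplete |
| After the POD 3 report, up to POD 7 | complete | complete |

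The first row is a problem under either window, and the second only under 72 hours. The third loses nothing primary.

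**Step 2. Whether another source fills the gap.** Section 3.4 describes one record access after surgery, and its opioid item is PACU consumption. Section 6.1 mentions diary entries, and the table of contents names a medication usage record. No section describes either as a source of the endpoint, or says how it would be recovered from someone who leaves. The POD 1–3 contacts are therefore the only described source for use at home.

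**Step 3. What then happens.** Under 4.2.5 the remaining contacts are not required. The outcome is incomplete, and 6.1 allows exclusion. Sections 3.6 and 6.1 nevertheless call the analysis intention-to-treat.

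**Step 4. The sample-size margin.** Section 6.3 states 42 per group (two-sided t test, α = 0.05, power 0.80, a moderate effect with no number given).

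- With d = 0.5 (assumed), the t test needs 64 per group and the normal approximation 63, so 42 is not reproduced.
- Solving back from 42 gives d = 0.619 by the t test. The normal formula gives (1.960 + 0.842) × √(2/42) = 0.611.
- The margin is 50 − 42 = 8 per arm, or 8/50 = 16%.
- At d = 0.619, power is 0.865 with 50 per arm, 0.827 with 45, 0.800 with 42 and 0.780 with 40. At d = 0.5 it is 0.697 with 50 and 0.620 with 42.

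The margin protects power. It gives no protection against bias from selective loss.

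**Step 5. An outer bound on bias.** Assume a normal outcome, losses in one arm only, and that those lost are exactly that arm's heaviest users. Removing the top fraction p lowers the arm's mean by φ(z₁₋ₚ)/(1 − p) standard deviations.

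| Lost of 50 | p | Shift (SD) | Share of d = 0.619 |
|---|---|---|---|
| 2 | 4% | 0.0862/0.96 = 0.090 | 15% |
| 4 | 8% | 0.1487/0.92 = 0.162 | 26% |
| 8 | 16% | 0.2433/0.84 = 0.290 | 47% |

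The fractions are illustrative; the documents give no withdrawal rate.

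**The case against.** A reader might infer something stronger: that the plan seeks nothing but vital status, bars follow-up and never requests home opioid use, so that every withdrawal after discharge costs a primary outcome. The documents do not support this, for four reasons.

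- Section 10.3 sets a minimum for what may be sought, and 4.2.5 makes follow-up optional rather than forbidden.
- Home use is requested on POD 1, 2 and 3 until the subject leaves, and 10.3 keeps what was collected before revocation.
- A subject who leaves after the last report in the primary window loses nothing primary. On the 24-hour window that point comes with the POD 1 report.
- Section 10.3 is a confidentiality clause for people who have withdrawn permission. Asking them for more health data would be a preference, not the correction of an error.

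There is also a practical objection. One question at the moment of withdrawal cannot cover hours that have not yet passed, so complete recovery needs later contact with someone who has withdrawn, and the subject may refuse.

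All of this stands, and it limits the point. It does not remove it. Text that merely permits follow-up does not direct anyone to collect the outcome, and no section separates stopping study visits from refusing all further data.

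**Conclusion.** The point holds as a minor, inexpensive improvement to 4.2.5. It applies to subjects who leave by choice after discharge and before the last report in the primary window. It rests on the POD 1–3 contacts being the only source for home use, and on 6.1 being applied as written.

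The size of the bias cannot be estimated. The documents give neither a withdrawal rate nor a link between leaving and pain. A reader might take the 47% in the working as the likely distortion. It is not: it puts all losses in one arm, makes them that arm's heaviest users, and uses a back-solved effect size. The 16% margin is not a forecast of voluntary withdrawal either, since 6.3 gives the extra subjects two purposes, dropout of any kind and added power. What can be said is that selective loss could matter, and that a larger enrolment does not remove it.

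The 24- versus 72-hour conflict decides how many withdrawals are affected, so it has to be settled together with this point.

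**What to change.** 1. In 4.2.5 and the consent form, separate two choices: (a) stopping study procedures or visits while permitting the remaining opioid-use reports to the end of the primary window, together with chart data; and (b) refusing all further data collection.
2. Have staff ask each withdrawing subject for permission for (a). If the subject agrees, record opioid use to date at withdrawal and make the remaining contacts through the end of the window.
3. State in 4.2.5 that data already collected are kept, as 10.3 does for revocation.
4. Reconcile the primary window across the Protocol Summary and sections 1.2, 1.3, 6.1 and 6.2, so that staff know which reports to ask for.
5. Leave 10.3 unchanged for subjects who fully revoke authorization, so that those who choose (b) are not questioned again.

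The cost is wording in 4.2.5 and the consent form, the window correction, and one or a few brief contacts with subjects who have withdrawn. They may decline, so recovery will be partial and its extent cannot be predicted.

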11.1 Data Collection and Management Responsibilities

Data collection is the responsibility of the clinical trial staff at the site under the supervision of the site PI. The investigator is responsible for ensuring the accuracy, completeness, legibility, and timeliness of the data reported.

All source documents should be completed in a neat, legible manner to ensure accurate interpretation of data. Black ink is required to ensure clarity of reproduced copies. When making changes or corrections, cross out the original entry with a single line, and initial and date the change. DO NOT ERASE, OVERWRITE, OR USE CORRECTION FLUID OR TAPE ON THE ORIGINAL.

Copies of the electronic CRF (eCRF) will be provided for use as source documents and maintained for recording data for each participant enrolled in the study. Data reported in the eCRF derived from source

CONFIDENTIAL

This material is the property of the NYU School of Medicine and Langone Medical Center. Do not disclose or use except as authorized in writing by the study sponsor

documents should be consistent with the source documents or the discrepancies should be explained and captured in a progress note and maintained in the participant's official electronic study record.

Clinical data (including AEs, concomitant medications, and expected adverse reactions data) and clinical laboratory data will be entered into Redcap. The data system includes password protection and internal quality checks, such as automatic range checks, to identify data that appear inconsistent, incomplete, or inaccurate. Clinical data will be entered directly from the source documents.

11.2 Study Records Retention

Study documents will be retained for the longer of 3 years after close-out, 5 years after final reporting/publication.

11.3 Protocol Deviations

A protocol deviation is any noncompliance with the clinical trial protocol, GCP, or Manual of Procedures (MOP) requirements. The noncompliance may be either on the part of the participant, the investigator, or the study site staff. As a result of deviations, corrective actions are to be developed by the site and implemented promptly.

These practices are consistent with ICH E6:

- 4.5 Compliance with Protocol, sections 4.5.1, 4.5.2, and 4.5.3
- 5.1 Quality Assurance and Quality Control, section 5.1.1
- 5.20 Noncompliance, sections 5.20.1, and 5.20.2.

It is the responsibility of the site PI/study staff to use continuous vigilance to identify and report deviations within 7 working days of identification of the protocol deviation, or within 7 working days of the scheduled protocol-required activity.

Protocol deviations must be reported to the local IRB per their guidelines. The site PI/study staff is responsible for knowing and adhering to their IRB requirements. Further details about the handling of protocol deviations will be included in the MOP.

11.4 Publication and Data Sharing Policy

The International Committee of Medical Journal Editors (ICMJE) member journals have adopted a clinical trials registration policy as a condition for publication. The ICMJE defines a clinical trial as any research project that prospectively assigns human subjects to intervention or concurrent comparison or control groups to study the cause-and-effect relationship between a medical intervention and a health outcome. Medical interventions include drugs, surgical procedures, devices, behavioral treatments, process-of-care changes, and the like. Health outcomes include any biomedical or health-related measures obtained in patients or participants, including pharmacokinetic measures and adverse events. The ICMJE policy, and the Section 801 of the Food and Drug Administration Amendments Act of 2007, requires that all clinical trials be registered in a public trials registry such as ClinicalTrials.gov, which is sponsored by the National Library of Medicine. Other biomedical journals are considering adopting similar policies. For interventional clinical trials performed under NIH IC grants and cooperative agreements, it is the grantee's responsibility to register the trial in an acceptable registry, so the research results may be considered for publication in ICMJE member journals. The ICMJE does not review specific studies to determine whether registration is necessary; instead, the committee recommends that researchers who have questions about the need to

CONFIDENTIAL

This material is the property of the NYU School of Medicine and Langone Medical Center. Do not disclose or use except as authorized in writing by the study sponsor

register err on the side of registration or consult the editorial office of the journal in which they wish to publish.

FDAAA mandates that a "responsible party" (i.e., the sponsor or designated principal investigator) register and report results of certain "applicable clinical trials":

- Trials of Drugs and Biologics: Controlled, clinical investigations, other than Phase I investigations of a product subject to FDA regulation;
- Trials of Devices: Controlled trials with health outcomes of a product subject to FDA regulation (other than small feasibility studies) and pediatric postmarket surveillance studies.
- NIH grantees must take specific steps to ensure compliance with NIH implementation of FDAAA.

12 Study Finances

12.1 Funding Source

There is no funding source available.

